4 SELECTION AND WITHDRAWAL OF PARTICIPANTS

4.1 Inclusion Criteria

Participants who meet all of the following criteria will be eligible to participate in the study:

- 1. Are willing and able to give written informed consent before initiation of any study-related procedures and willing to comply with all required study procedures;
- 2. Are male or female and ≥ 18 years of age at Screening (Visit 1);
 - o Females may be enrolled if all 3 of the following criteria are met:
 - They are not pregnant;
 - They are not breastfeeding; and
 - They do not plan on becoming pregnant during the study.
 - Females of childbearing potential must have a negative urine pregnancy test at Screening (Visit 1);

Note: Females are not considered to be of childbearing potential if they meet 1 of the following criteria as documented by the Investigator:

- They have had a hysterectomy or tubal ligation at a minimum of 1 cycle prior to signing the ICF; or
- They are postmenopausal, defined as ≥1 year since their last menstrual period for females ≥55 years of age or ≥1 year since their last menstrual period and have a follicle-stimulating hormone (FSH) level in the postmenopausal range at Screening (Visit 1) for females <55 years of age.

- Females of childbearing potential must agree to use an effective method of avoiding pregnancy from Screening (Visit 1) until 35 days after the last dose of a study drug. Males whose partners are of childbearing potential must agree to use an effective method of avoiding pregnancy from Screening (Visit 1) until 35 days after the last dose of a study drug. Effective methods of avoiding pregnancy are contraceptive methods used consistently and correctly (including implantable contraceptives, injectable contraceptives, oral contraceptives, transdermal contraceptives, intrauterine devices, and barrier methods) or a sterile sexual partner.
- 3. Have underlying HeFH and/or a history of ASCVD or multiple ASCVD risk factors;

Diagnosis of HeFH:

Diagnosis must be made by either prior historical genotyping or by clinical assessment using either the WHO Criteria/Dutch Lipid Clinical Network Criteria with a score that is ≥3 points, as specified in Appendix C or the Simon Broome Register Diagnostic Criteria with an assessment of "Possible HeFH" or "Definite HeFH," as specified in Appendix D.^{23,24} Participants with a diagnosis of HeFH may or may not have a history of ASCVD or ASCVD-risk equivalents;

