4.5 Withdrawal Criteria

A participant may prematurely discontinue study drug and/or withdraw from the study at any time. However, a distinction must be made between premature discontinuation of study drug and withdrawal from the study. All efforts should be made to ensure the participant continues in the study per protocol. If a participant discontinues study drug prior to completion of the study, all efforts will be made to continue to follow the participant and collect data for all visits.

Only participants that request discontinuation from the study and withdraw consent will be considered withdrawn from the study. For safety reasons, it will be recommended that all participants who withdraw from the study complete an End of Treatment (EOT) Visit. Withdrawn participants will not be replaced.

Participants may need to discontinue study drug during the course of the study. All efforts will be made to restart the study drug; however, in the event of the following, participants may be permanently discontinued from study drug:

- Occurrence of any medical condition or circumstance that exposes the participant to substantial risk and/or does not allow the participant to adhere to the protocol-specified study drug treatment regimen;
- Any SAE, clinically significant AE, severe laboratory abnormality, intercurrent illness, or other medical condition, which indicates to the Investigator that continued treatment with study drug is not in the best interest of the participant;
- Pregnancy; or
- Requirement of prohibited concomitant medication.

If a participant permanently discontinues study drug, he/she will continue to participate in study visits as described below:

- If a participant discontinues study drug between Visit 2 (Day 1) and Visit 3 (Day 28) or at Visit 3 (Day 28), he/she should complete an EOT Visit at Day 28, return to complete Visit 4 (Day 84), and return to complete the Safety Follow-up Visit (Day 112); or
- If a participant discontinues study drug between Visit 3 (Day 28) and Visit 4 (Day 84), he/she should return for Visit 4 (Day 84) and the Safety Follow-up Visit (Day 112) as scheduled.

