5.5.3 Study Drug Administration

Study drugs (2 tablets and 1 capsule) will be administered by the participant orally with water, with or without food, once daily on Day 1 to Day 84 at approximately the same time each morning. On days with visits scheduled, participants should not take the study drugs prior to the visit but should bring the study drugs with them to the site. The study drugs will be administered with water following all fasted blood samples. At Visit 3 (Day 28) and Visit 4 (Day 84), participants will dose from the kit received at the previous visit (Visit 2 [Day 1] and Visit 3 [Day 28], respectively).

If a participant forgets to take the study drugs on a given day, he/she should take the next dose as normal and should not take a double dose to make up for the forgotten dose.

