6 STUDY PROCEDURES

Study procedures will follow the Schedule of Procedures (Appendix A).

Unscheduled visits may be scheduled as needed per the judgment of the Investigator. Procedures will be determined based on the reason for the visit.

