8.7.2 Endocrinology Assessments

A urine pregnancy test will be performed for women of childbearing potential at Screening (Visit 1) prior to their participation in the study, at Visit 4 (Day 84), and at an EOT Visit, in cases of early discontinuation of study drug or study.

An FSH test will be performed at Screening (Visit 1) prior to participation in the study in women <55 years of age for whom it has been ≥1 year since their last menstrual period.

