- b. A participant who is screened and does not meet the study eligibility criteria may be considered for rescreening upon Sponsor and/or Medical Monitor consultation and approval. Rescreened participants will be assigned a new participant number. Rescreening should occur no less than 5 days after the last screening visit.
- c. Participants who discontinue study drug between Visit 2 (Day 1) and Visit 3 (Day 28) or at Visit 3 (Day 28) should complete an EOT Visit at Day 28, return to complete Visit 4 (Day 84), and return to complete the Safety Follow-up Visit (Day 112). In addition, participants who withdraw from the study should complete an EOT Visit. Participants who discontinue study drug between Visit 3 (Day 28) and Visit 4 (Day 84) will not undergo an EOT Visit but continue with study visits per protocol.
- d. Participants will be required to sign an ICF before any study-related procedures are performed.
- e. Confirm the participant continues to meet the inclusion and exclusion criteria and assess any updates since Screening (Visit 1).
- f. Weight and height will be measured at Screening (Visit 1) and will be used to calculate body mass index. Measurement of weight should be performed with the participant dressed in indoor clothing, with shoes removed.
- g. The physical examination should comprise a focused examination, which includes general, respiratory, CV, abdominal, and extremities evaluations.
- h. Vital signs will include body temperature, heart rate, and triplicate blood pressure (systolic and diastolic) measurements. Participants should be in the supine position after at least 10 minutes rest prior to the vital sign measurements.
- i. A single 12-lead ECG will be performed in the supine position after 10 minutes of rest. ECGs are to be assessed for clinical significance by a qualified medical designee at the study site.
- j. For women of childbearing potential only.
- k. FSH test will be performed in women <55 years of age for whom it has been ≥1 year since their last menstrual period.
- 1. At Screening (Visit 1), Visit 4 (Day 84), and EOT, chemistry panel will include HbA1c.

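### Optional, cheap safety improvement: the only pregnancy test before first dose is at Screening, 1 to 14 days earlier, and no test supports the Visit 2 re-check that a woman is not pregnant

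*Protocol*

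**What the plan says.** Inclusion criterion 2 (Protocol 4.1) lists, among the conditions for enrolling women, "They are not pregnant". It supports this with a test: "Females of childbearing potential must have a negative urine pregnancy test at Screening (Visit 1"). Section 8.7.2 repeats the timing: "A urine pregnancy test will be performed for women of childbearing potential at Screening (Visit 1) prior to their participation in the study", then again at Visit 4 (Day 84) and at an EOT Visit after early discontinuation. Appendix A and SAP Table 1 mark the test at the same three points and leave Visits 2, 3 and 5 blank. Under Appendix A note c, a woman who stays on study drug and in the study has no EOT Visit, so her scheduled tests are Screening and Visit 4 only.

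At Visit 2, Appendix A note e tells the site: "Confirm the participant continues to meet the inclusion and exclusion criteria and assess any updates since Screening (Visit 1").

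The other protections are these:

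- Women who plan a pregnancy during the study are not eligible (4.1).
- Contraception is mandatory: "Females of childbearing potential must agree to use an effective method of avoiding pregnancy from Screening (Visit 1") to 35 days after the last dose.
- Pregnancy is one of the events in section 4.5 for which "participants may be permanently discontinued from study drug".
- Section 8.4 stops dosing at once when a participant becomes pregnant.
- Section 6 allows extra visits: "Unscheduled visits may be scheduled as needed per the judgment of the Investigator".

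**The concern.** Visit 2 is the last point at which exposure can be prevented altogether. The site must confirm there that the woman still meets the not-pregnant criterion, but the only objective evidence it holds is a urine result that may be two weeks old.

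Contraception begins at Screening. It cannot act on a conception that happened shortly before Screening and was too early for the Screening test to show. Such a pregnancy could become detectable between Screening and Day 1, and nothing scheduled at Visit 2 would find it. The stop-dosing rule in 8.4 works only once the pregnancy is known.

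What is at stake is embryo-fetal exposure that one inexpensive test could sometimes avoid. Efficacy, sample size and power are not affected.

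**Working it through.** The plan gives no figure of its own here, so there is nothing to reproduce. The check is day arithmetic on the schedule.

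Inputs:

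- Screening falls on Day −14 to Day −1 (Appendix A).
- There is no Day 0 (SAP 3.1.1), so Day −k is k days before Day 1, and Day d is d − 1 days after it.
- Dosing runs from Day 1 to Day 84 (Protocol 5.5.3).
- Visit 4 is Day 84 ± 7, that is Day 77 to Day 91 (Appendix A).
- Assumption: the Screening test is done on the day of the Screening visit.

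**Age of the last negative test at first dose.** It is 1 day if Screening is on Day −1 and 14 days if it is on Day −14. With a test at Visit 2 it is 0 days.

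**Interval between consecutive scheduled tests, for a woman who keeps dosing.** Days after Day 1 are 77 − 1 = 76, 84 − 1 = 83 and 91 − 1 = 90.

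| | Visit 4 on Day 84 | Visit 4 anywhere in Day 77 to 91 |
|---|---|---|
| Now | 1 + 83 = 84 to 14 + 83 = 97 days | 1 + 76 = 77 to 14 + 90 = 104 days |
| With a Day 1 test (longest remaining interval) | 83 days | 76 to 90 days |

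The reduction is exactly the 1 to 14 undosed days before first dose. The on-treatment part (83 days nominal) is unchanged.

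**Feasibility at Visit 2.** Appendix A already collects urine at Visit 2 for the albumin-creatinine ratio. Section 5.5.3 already holds the visit-day dose until after sampling: "The study drugs will be administered with water following all fasted blood samples". A dipstick can be read in that time.

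**Expected benefit.** Exposures avoided = (number of women of childbearing potential) × (probability of a pregnancy that is negative at Screening and positive on Day 1). The documents give neither factor, so no number can be computed.

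**The case against.** The strongest objection is that nothing in the plan is broken. The criterion asks for a negative test at Screening and the schedule delivers it. Note e asks for eligibility to be confirmed and updates assessed; it does not call for repeat testing. Other laboratory criteria (LDL-C, triglycerides, eGFR, liver enzymes, HbA1c, CK) are also tied to Screening alone. All of this stands. A reader might infer an inconsistency between the eligibility text and the schedule, but the documents do not support that: all four places agree. The point survives only as an improvement. Re-measuring at Visit 2 would not be foreign to this design, since exclusion criterion 4 already names blood pressure at both Screening and Randomization.

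A reader might also infer that every existing protection depends on someone suspecting a pregnancy. That is not so. The exclusion of women planning pregnancy and the contraception rule are preventive and need no suspicion. Only discontinuation, the stop-dosing rule and, in practice, an unscheduled test depend on knowledge or suspicion.

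A third tempting argument is that by a nominal Day 84 visit 83 of the 84 planned doses have been taken (83/84 = 98.8%). That is correct for Day 84, although a Day 77 visit follows only 76 doses. In any case it describes the on-treatment gap, which a Day 1 test does not shorten. A pregnancy conceived after Day 1 would be found no sooner. The figure therefore does not measure the benefit of this fix.

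**Conclusion.** The point holds as an optional patient-safety improvement, and not as an error in the plan. The measurable gain is that the last negative test at first dose goes from 1 to 14 days old to 0 days old. The gain is largest when Screening was close to 14 days earlier and small when it was the day before.

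It would be too strong to say that a Day 1 test closes the pre-dose gap. The limit that allows an early pregnancy to be missed at Screening applies on Day 1 as well, and the documents give no detection time or sensitivity for the test. It narrows the gap.

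Confidence is high in the schedule facts and the day arithmetic. The size of the benefit is unknown: the number of women of childbearing potential is not stated, and the drug's properties are referred to the Investigator's Brochure. The number of exposures avoided is likely very small.

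**What to change.** Add a urine pregnancy dipstick at Visit 2 (Day 1) for women of childbearing potential, with a negative result required before randomization and first dose. Four edits are needed: name Visit 2 alongside Screening in inclusion criterion 2, add it to section 8.7.2, and add a mark under Visit 2 in both Appendix A and SAP Table 1.

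The cost per woman is one dipstick at an existing visit that already collects urine, with no extra visit and no invasive procedure. There will be a rare Day 1 screen failure. The larger cost is administrative: section 12.1 requires an amendment to pass the same review and approval as the original protocol, and it must then reach about 60 sites. It is best bundled with another amendment.

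Shortening the on-treatment interval is a separate choice. With a further test at Day 28 the longest interval would be 84 − 28 = 56 days nominal, or 91 − 21 = 70 days at worst within the visit windows. The documents do not allow the benefit of that test to be quantified, and this recommendation does not depend on it.

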4.2 Exclusion Criteria

Participants who meet any of the following criteria will be excluded from participation in the study:

- 1. Have current or any previous history of New York Heart Association class III or IV heart failure or left ventricular ejection fraction <30%;
- 2. Have been hospitalized for heart failure within 5 years prior to Screening (Visit 1);
- 3. Have had any of the following clinical events within 3 months prior to Screening (Visit 1):
 - o Non-fatal MI;
 - Non-fatal stroke;
 - Non-elective coronary revascularization; and/or
 - Hospitalization for unstable angina and/or chest pain.
- 4. Have uncontrolled severe hypertension, defined as either systolic blood pressure ≥160 mmHg or diastolic blood pressure ≥100 mmHg at both Screening (Visit 1) and Randomization (Visit 2 [Day 1]) taken as the average of triplicate measurements. One triplicate retest will be allowed during the same visit, at which point if the retest result is no longer exclusionary, the participant may be randomized;
- 5. Have a formal diagnosis of homozygous FH;
- 6. Have active liver disease, defined as any known current infectious, neoplastic, or metabolic pathology of the liver; Child-Pugh score of 7 to 9 (Class B) or 10 to 15 (Class C); unexplained elevations in alanine aminotransferase (ALT) or aspartate aminotransferase (AST) > 3 × upper limit of normal (ULN); or total bilirubin > 2 × ULN at Screening (Visit 1);
 - Note: An abnormal ALT, AST, or total bilirubin must be confirmed by a repeat abnormal measurement at least 1 week apart.
- 7. Have a glycosylated hemoglobin (HbA1c) ≥10.0% (≥0.100 hemoglobin fraction) or a fasting glucose ≥270 mg/dL (≥15.0 mmol/L) at Screening (Visit 1);
- 8. Have thyroid-stimulating hormone $\geq 1.5 \times ULN$ at Screening (Visit 1);
- 9. Have creatine kinase (CK) $>3 \times$ ULN at Screening (Visit 1);
- 10. Have a history of a malignancy that required surgery (excluding local and wide local excision), radiation therapy, and/or systemic therapy during the 3 years prior to Randomization (Visit 2 [Day 1]);
- 11. Have a known history of alcohol and/or drug abuse within 5 years prior to Randomization (Visit 2 [Day 1]);
- 12. Have received treatment with other investigational products or devices within 30 days of Screening (Visit 1) or 5 half-lives of the previous investigational product, whichever is longer;
 - Note: Participants who have received treatment for COVID-19 with standard of care and/or emergency use authorization medications, including vaccinations and boosters, within 30 days of Screening (Visit 1) or 5 half-lives of the previous investigational product **will** be permitted.
- 13. Are taking gemfibrozil or have taken gemfibrozil within 30 days of Screening (Visit 1);

- 14. Are taking ezetimibe or have taken ezetimibe within 14 days of Screening (Visit 1);
- 15. Have planned use of other investigational products or devices during the course of the study;
- 16. Have participated in any clinical study evaluating obicetrapib;
- 17. Have a known allergy or hypersensitivity to the study drugs, placebo, or any of the excipients in the study drugs or placebo; or
- 18. Have any participant condition that, according to the Investigator, could interfere with the conduct of the study, such as, but not limited to, the following:
 - o Are unable to communicate or to cooperate with the Investigator;
 - Are unable to understand the protocol requirements, instructions and study-related restrictions, and the nature, scope, and possible consequences of the study (including participants whose cooperation is doubtful due to drug abuse or alcohol dependency);
 - Are unlikely to comply with the protocol requirements, instructions, and study-related restrictions (eg, uncooperative attitude, inability to return for follow-up visits, and improbability of completing the study);
 - o Have any medical or surgical condition which, in the opinion of the Investigator, would put the participant at increased risk from participating in the study; or
 - o Are directly involved in the conduct of the study.

4.3 Retesting

If laboratory abnormalities during the Screening Period are considered by the Investigator to be transient, then the laboratory tests may be repeated once during the Screening Period. The Investigator's rationale for retesting should be documented. If the retest result is no longer exclusionary, the participant may be randomized.

4.4 Rescreening

A participant who is screened and does not meet the study eligibility criteria may be considered for rescreening upon Sponsor and/or Medical Monitor consultation and approval. Rescreened participants will be assigned a new participant number. Rescreening should occur no less than 5 days after the last screening visit.

4.5 Withdrawal Criteria

A participant may prematurely discontinue study drug and/or withdraw from the study at any time. However, a distinction must be made between premature discontinuation of study drug and withdrawal from the study. All efforts should be made to ensure the participant continues in the study per protocol. If a participant discontinues study drug prior to completion of the study, all efforts will be made to continue to follow the participant and collect data for all visits.

Only participants that request discontinuation from the study and withdraw consent will be considered withdrawn from the study. For safety reasons, it will be recommended that all participants who withdraw from the study complete an End of Treatment (EOT) Visit. Withdrawn participants will not be replaced.

Participants may need to discontinue study drug during the course of the study. All efforts will be made to restart the study drug; however, in the event of the following, participants may be permanently discontinued from study drug:

- Occurrence of any medical condition or circumstance that exposes the participant to substantial risk and/or does not allow the participant to adhere to the protocol-specified study drug treatment regimen;
- Any SAE, clinically significant AE, severe laboratory abnormality, intercurrent illness, or other medical condition, which indicates to the Investigator that continued treatment with study drug is not in the best interest of the participant;
- Pregnancy; or
- Requirement of prohibited concomitant medication.

If a participant permanently discontinues study drug, he/she will continue to participate in study visits as described below:

- If a participant discontinues study drug between Visit 2 (Day 1) and Visit 3 (Day 28) or at Visit 3 (Day 28), he/she should complete an EOT Visit at Day 28, return to complete Visit 4 (Day 84), and return to complete the Safety Follow-up Visit (Day 112); or
- If a participant discontinues study drug between Visit 3 (Day 28) and Visit 4 (Day 84), he/she should return for Visit 4 (Day 84) and the Safety Follow-up Visit (Day 112) as scheduled.

If a participant who discontinues study drug will not or does not return for 1 or all future visits, efforts should be made to collect as much information as possible via a telephone call, conducted at the same time as the planned study visit(s). The efforts to follow-up via telephone at each planned visit day should continue through the day of the planned Safety Follow-up Visit (Day 112).

When participants enter the study, contact information and alternative methods of contact will be collected in the event that the site loses contact with the participant. In the case of a participant lost to follow-up, attempts to contact the participant must be made and documented in the participant's medical records.

The Sponsor or regulatory agency can terminate the study at any time for any reason.

5 STUDY TREATMENTS

5.1 Treatment Groups

Participants will be randomized in a 1:1:1:1 ratio to 1 of the following treatment groups:

- FDC therapy: Obicetrapib 10 mg + ezetimibe 10 mg (administered as 1 obicetrapib 10 mg + ezetimibe 10 mg FDC tablet, 1 obicetrapib-matched placebo tablet, and 1 ezetimibe-matched placebo capsule);
- Obicetrapib monotherapy: Obicetrapib 10 mg (administered as 1 FDC-matched placebo tablet, 1 obicetrapib 10 mg tablet, and 1 ezetimibe-matched placebo capsule);
- Ezetimibe monotherapy: Ezetimibe 10 mg (administered as 1 FDC-matched placebo tablet, 1 obicetrapib-matched placebo tablet, and 1 ezetimibe 10 mg capsule [over-encapsulated 10 mg tablet]); or
- Placebo (administered as 1 FDC-matched placebo tablet, 1 obicetrapib-matched placebo tablet, and 1 ezetimibe-matched placebo capsule).

